11. DATA ANALYSIS

All data will be analyzed using SPSS version 28.0. For quantitative data, we will use the statistical test ANOVA and for descriptive statistics we will use means and standard deviations. Also, an expert statistician will be consulted to accurately analyze and interpret the results. The alpha level will be set at 0.05.

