Data was analyzed using SPSS version 28.0. Assuming a moderate effect size of 0.3, a power of 0.80, an alpha of 0.05 and 15% dropout rate, the estimated sample size was 40 participants. Data was summarized using frequency (%) for qualitative variables, mean \pm standard deviation (SD) for continuous variables, and median (minimum, maximum) when the distribution was not approximately normal. The normality of the outcome variables was examined using the Shapiro wilk test and boxplots. The frequency distribution of gender between the two study groups was compared using Fisher's exact test. Mean baseline characteristics and outcome variables by study group was examined using independent t-test. Median VAS, NDI, and JPE rotation right were compared between the intervention and control groups using Mann-Whitney U test. For each study group, changes in mean outcome variables (cervical spine AROM, anxiety, neck proprioception, VAS, NDI) over time (post versus pre) were examined using paired t-test or Wilcoxon signed rank test when the distribution is not approximately normal. Changes in outcome variables by group (intervention versus control) overtime (post 2 weeks versus pre) were assessed using 2x2 mixed factorial analysis of variance (ANOVA). If there was a significant interaction between group and time, the changes are significantly different between the two groups. There was a significant difference in mean STAI_T and lateral flexion left between the intervention and control groups at baseline, thus this was controlled for baseline differences using analysis of covariance (ANCOVA). In the intervention group, we examined changes in outcome variables over time (pre versus post 30 minutes versus post 2 weeks) using repeated measures ANOVA or Friedman's test if the data was not approximately normal. If the results were significant, Bonferroni's post hoc comparisons were conducted, or Wilcoxon signed rank test were used to determine what times were significantly different. The level of significance was set at $p \leq 0.05$.

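### Between-arm change in VAS, NDI and JPE is decided by an unadjusted ANOVA interaction; one baseline-adjusted test for every outcome would give more power at little cost

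*SAP*

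**What the plan says.** The protocol (section 11, Data Analysis) is brief: "For quantitative data, we will use the statistical test ANOVA", and "The alpha level will be set at 0.05".

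The SAP, a single paragraph, adds the following.

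- **Normality.** "The normality of the outcome variables was examined using the Shapiro wilk test and boxplots". Change scores and model residuals are not mentioned.
- **Between arms, rank test.** "Median VAS, NDI, and JPE rotation right were compared between the intervention and control groups using Mann-Whitney U test". No time point is given. The sentence before it applies t-tests to baseline characteristics and outcome variables.
- **Within arms.** Paired t-test or Wilcoxon. For the three time points in the intervention arm, repeated measures ANOVA or Friedman.
- **Between arms, change.** Changes by group over time "were assessed using 2x2 mixed factorial analysis of variance (ANOVA"). A significant interaction is read as a difference in change between arms. No rank version and no baseline adjustment are stated.
- **ANCOVA.** Used for STAI_T and lateral flexion left, because these differed significantly between arms at baseline.

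**The concern.** For VAS, NDI and JPE rotation right, the interaction is the only between-arm test of change in the SAP. With two time points it is the same test as a two-sample t-test on change scores. That test uses the baseline value by plain subtraction, which is inefficient unless the pre-post correlation is close to 1.

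The SAP already has the better tool, but reserves it for two outcomes that showed an observed baseline difference. Random imbalance is not what makes adjustment worthwhile; the correlation between baseline and follow-up is, and that applies to every outcome. Selecting by imbalance also means that outcomes in the same trial are judged by different models for a data-dependent reason.

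The normality check looks at the wrong quantity. The paired t-test and the interaction depend on the distribution of changes or residuals, not of raw scores.

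At stake is power in a trial with about 17 analysable participants per arm, and clarity about which between-arm result counts.

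**Working it through.** **1. The plan's own sample size.** Inputs from the SAP: "Assuming a moderate effect size of 0.3", "a power of 0.80", "an alpha of 0.05 and 15% dropout rate", total 40. The effect-size metric, the test and the correlation are not stated. I read 0.3 as Cohen's f for the 2x2 interaction, assume a two-sided test and take rho = 0.3.

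- Noncentrality = N × f² × 2 / (1 − rho) = 34 × 0.09 × 2 / 0.7 = 8.74, with 1 and 32 df. Power is 0.818.
- Dropout: 34 / 0.85 = 40, which matches.

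The match is not unique. After dropout, f = 0.3 gives 55, 45, 29 and 19 at rho = 0, 0.2, 0.5 and 0.7, while f = 0.25 with rho = 0.5 also gives 40. What carries forward is 40 × 0.85 = 34, or 17 per arm.

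**2. Why adjustment helps.** With equal variance σ² at both times, the variance per participant is:

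- change score: 2(1 − rho)σ²
- ANCOVA: (1 − rho²)σ²

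The ratio of ANCOVA to change score is (1 + rho)/2 = 0.65, 0.75 and 0.85 at rho = 0.3, 0.5 and 0.7. The change-score test therefore needs 1/0.65 = 1.54, 1.33 and 1.18 times as many participants for the same precision. This does not depend on skewness.

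**3. Power under skewed VAS.** Assumptions: log-normal VAS, entry below 4 (protocol section 8c), 17 per arm. Strong skew is median 1.5 cm with log-SD 0.6; milder skew is median 2.0 cm with log-SD 0.4. Entries are power in % at rho 0.3/0.5/0.7, from 1,500 trials per cell for the two strong-skew rows and 2,000 for the milder row.

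| Scenario | ANOVA interaction | ANCOVA | Rank ANCOVA |
|---|---|---|---|
| Strong skew, −0.6 cm | 29/38/56 | 36/42/60 | 50/58/76 |
| Strong skew, 40% reduction | 43/58/72 | 61/70/83 | 67/76/87 |
| Milder skew, −0.6 cm | 42/54/72 | 53/62/75 | 62/68/79 |

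Gains over the interaction, in points:

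- ANCOVA: 7/4/4, 18/12/11 and 11/8/3, so 3 to 18.
- Rank ANCOVA: 21/20/20, 24/18/15 and 20/14/7, so 7 to 24.

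The Monte Carlo standard error is at most √(0.25/1500) = 1.3 points per cell.

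**4. Is the parametric form the cause?** Replacing the interaction by Mann-Whitney on change, without adjustment, gives (2,000 trials per cell, each set against the ANOVA in the same run):

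- strong skew, −0.6 cm: 34/43/62 against 31/38/54
- strong skew, 40% reduction: 44/55/74 against 45/56/74
- milder skew, −0.6 cm: 43/55/75 against 42/54/72

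That is −1 to +8 points, little in most cells. A more heavily skewed JPE-like outcome (skewness about 2.3) gained 4 to 12 points.

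A separate check used the design effect (f = 0.3, a difference in change of 1.2 SD) at rho 0.3, with VAS-like values floored at 0. The interaction had 0.49 to 0.65 power and Mann-Whitney on change 0.51 to 0.64, so both lose almost equally. For VAS-like and NDI-like outcomes together under the same floor, ANCOVA had 0.75 to 0.87 and rank ANCOVA 0.92 to 0.95.

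**5. Validity and the normality check.** Under no effect the interaction rejected in 4.7 to 5.5% of trials at 17 to 20 per arm, with outcome skewness of 0.6 to 2.3. The skewness of the change was then about 0, because the difference of two similarly distributed measurements is roughly symmetric. Raw-score skewness is therefore a poor guide to whether the interaction or the paired t-test is suitable.

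**6. Two readings of the Mann-Whitney sentence.**

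- Baseline only: it is no test of effect, and nothing competes with the interaction.
- Follow-up included: claiming an effect if either test is significant gives about 8 to 10% error under no effect. Under a 40% reduction with strong skew and the entry cut, the two tests differ in about 35 to 38% of trials.

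**The case against.** The defence is substantial.

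- **The planned test is sound.** It holds its error rate. A reader might infer from the rank tests that a parametric ANOVA on these outcomes is invalid, or weak because it is parametric. The documents do not support that: the SAP reports nothing about the distribution of changes, and step 4 shows that ranking the change alone recovers little in most scenarios. This stands.
- **A contradictory verdict is not established.** A reader might infer that pain and disability carry two competing tests. The Mann-Whitney sentence follows the one on baseline t-tests and can be read as its non-normal counterpart at baseline. Even on the other reading, the SAP names the interaction as its criterion for change. What remains is that the time point is missing and that no sentence says how a follow-up Mann-Whitney result would be used.
- **The SAP already uses ANCOVA.** True, but only for two outcomes, triggered by an observed difference.
- **Rank ANCOVA is a preference.** Partly true. For the 40% reduction, ordinary ANCOVA recovers much of the gain (18 of 24 points at rho 0.3). Ranks add clearly more for the fixed shift under strong skew. That is why rank ANCOVA can serve either as the specified version or as a sensitivity analysis.
- **No primary outcome is named in either document**, so VAS and NDI cannot be called the main outcomes on documentary grounds. The point therefore applies to every outcome alike.

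**Conclusion.** The concern holds as a matter of efficiency and consistency, not validity. The unadjusted interaction is a legitimate test that gives away power. Under the assumed VAS distributions, ANCOVA adds about 3 to 18 points and rank ANCOVA about 7 to 24. The general variance ratio of 0.65 to 0.85 points the same way without any assumption about skewness. Much of the loss comes from the unadjusted change score rather than from using a parametric test.

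The error rate of about 8 to 10% is conditional: it needs the Mann-Whitney test to cover follow-up values and the analyst to choose between the two results.

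All power figures rest on assumed distributions, effects and correlations of 0.3 to 0.7, because the documents give no SD, skewness or correlation. The direction is more secure than the size. This is worth changing because the data needed are already collected.

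**What to change.** - Make one baseline-adjusted analysis, follow-up value on baseline value and arm, the deciding between-arm test for every outcome. Apply it alike to all JPE directions, and do not trigger it by observed imbalance or a normality test.
- For floor-bounded VAS and NDI, pre-specify rank ANCOVA (rank of follow-up on rank of baseline, residuals compared between arms) either as the deciding version or as a sensitivity analysis, and say which.
- State the time point of the Mann-Whitney comparison and limit it to description.
- Check residuals or changes rather than raw scores.
- Report the protocol's ANOVA for every outcome as a sensitivity analysis.
- State the effect-size metric, the test and the correlation behind the sample size of 40.

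The SAP is written in the past tense and reports a baseline finding, so date the change and report the stated ANOVA beside the new analysis.

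Cost: SAP wording and a few lines of SPSS syntax, with no new data. The drawback is that a rank p-value is on a different scale from the effect estimate. Giving a Hodges-Lehmann difference in change with its 95% confidence interval beside it keeps the result readable in scale units.

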Participants in the normal group will not receive any interventions in the lab or at home and will not receive education on the use of TENS equipment.

Participants in the control group will not receive any interventions in the lab or at home and will not receive education on the use of TENS equipment.

Participants in the intervention group with daily SMS text message reminders will be provided with a TENS unit by the investigators for home use for a total of 29 days and instructed by a licensed physical therapist for its use and safety. In addition, you will be provided with a daily log sheet to track its use while receiving SMS text message reminders for compliance. Then, the participants in this intervention group will receive a 30-minute high-frequency sensory TENS treatment in lab on the pain site in the neck and upper quadrant area. After the 30-minute high-frequency sensory TENS treatment, the participants in the intervention group will again complete the VAS, STAI, and NDI. Also, cervical spine proprioception will be measured with Noraxon myoMotionTM system instrument utilizing the JPE test.

Participants in the intervention group without daily SMS text message reminders will be provided with a TENS unit by the investigators for home use for a total of 29 days and instructed by a licensed physical therapist for its use and safety. In addition, you will be provided with a daily log sheet to track its use without receiving SMS text message reminders for compliance. Then, the participants in this intervention group will receive a 30-minute high-frequency sensory TENS treatment in lab on the pain site in the neck and upper quadrant area. After the 30-minute high-frequency sensory TENS treatment, the participants in the intervention group will again complete the VAS, STAI, and NDI. Also, cervical spine proprioception will be measured with Noraxon myoMotionTM system instrument utilizing the JPE test.

Session 2 (1st follow up) (Day 8): Participants will return on day eight. Participants in the normal group will be asked to complete again complete the VAS, STAI, and NDI. Also, cervical spine proprioception will be measured with Noraxon myoMotionTM system instrument utilizing the JPE test. Participants will not receive any interventions in the lab.

Participants in the control group will be asked to complete again complete the VAS, STAI, and NDI. Also, cervical spine proprioception will be measured with

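### Within-arm tests of change are not marked as descriptive, so significance in the TENS arm alone could be reported as a TENS effect

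*SAP*

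**What the plan says.** The SAP is a single paragraph. On change within arms it says: "For each study group, changes in mean outcome variables". These are tested from pre to post, for cervical range of motion, anxiety, proprioception, VAS and NDI, by a paired t-test, or a Wilcoxon signed rank test where the distribution is not approximately normal.

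It then plans a 2x2 mixed ANOVA of group by time and gives a reading rule: "If there was a significant interaction between group and time, the changes are significantly different between the two groups". ANCOVA is added for STAI_T and left lateral flexion, which differed between arms at baseline.

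For skewed outcomes it says: "Median VAS, NDI, and JPE rotation right were compared between the intervention and control groups using Mann-Whitney U test". No time point is given, and this is not described as a test of change.

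One significance level, p ≤ 0.05, covers all of these tests. No sentence ranks the within-arm tests below the interaction or calls them descriptive.

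The Protocol (section 8, part c) makes the control arm untreated: "Participants in the control group will not receive any interventions in the lab or at home".

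**The concern.** A within-arm p-value asks whether anything changed in that arm. The cause could be natural course, practice on the joint position error test, selection on entry pain, or TENS. The untreated arm is there to remove everything but TENS, and a paired test inside the TENS arm does not use it. Setting two within-arm verdicts side by side does not repair this, because a significant result beside a non-significant one is not a test of the difference.

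With about 17 completers per arm, paired tests have middling power for moderate changes. Two arms with the same true change will therefore often split into one significant and one not. At stake is a positive statement about TENS that the trial's own between-arm test does not support.

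The gap is wider for non-normal outcomes. The rank-based tests of change in the SAP are all within-arm: Wilcoxon in each arm, and Friedman with Wilcoxon follow-up in the intervention arm. The SAP does not say whether the mixed ANOVA is also used for these outcomes. A result that ignores the control arm could become the main evidence on change for pain and disability.

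**Working it through.** The plan gives no error rate for this pattern, so there is no figure of its own to reproduce.

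**Inputs from the documents**
- 20 per arm (Protocol, section 7); 15% dropout (Protocol, section 6, and SAP). 20 × 0.85 = 17 per arm.
- Alpha 0.05 per test (SAP). Sidedness is not stated; two-sided is assumed.

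**Assumptions, not in the documents**
- Both arms have the same true change, so TENS has no effect. Its size d, in SDs of change, runs from 0 to 0.7.
- Change scores are normal with equal SD in the two arms.

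**Formulas**
- Probability that one arm shows significant improvement: p = P(T > t₀.₉₇₅,₁₆), where T is noncentral t with 16 degrees of freedom and noncentrality d√17.
- Probability that one arm is significant in either direction: s.
- The arms are independent, so P(TENS significantly improved, control not significant) = p(1 − s).

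**Results, 17 per arm**

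| Shared improvement d | p | s | p(1 − s) |
|---|---|---|---|
| 0 | 0.025 | 0.050 | 0.024 |
| 0.3 | 0.213 | 0.214 | 0.167 |
| 0.5 | 0.491 | 0.491 | 0.250 |
| 0.7 | 0.773 | 0.773 | 0.175 |

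The maximum is 25%, reached when each arm has about an even chance of significance (d near 0.5). With the full 20 per arm the values at d = 0, 0.3, 0.5 and 0.7 are 2.4%, 18.6%, 24.6% and 13.2%.

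**Comparator.** In 100,000 simulated trials per setting (d from 0 to 0.5), the interaction test, which is a t-test on change scores, was significant in 4.9% to 5.1% of trials two-sided. It favoured TENS in 2.4% to 2.5%, against the exact 2.5%. The shared change cancels from the between-arm difference, so this rate does not depend on d.

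**Agreement between the two.** With 17 per arm, when the split pattern appeared, the interaction was also significant in 12.7% of cases at d = 0.3 and 9.6% at d = 0.5.

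**VAS.** Section 8 of the Protocol requires a VAS below 4/10 from the pain groups at entry. Selecting on a low score shifts the later mean upward, which is worsening. Assume a log-normal VAS with median 1.5 to 3 cm and pre-post correlation 0.3 to 0.7; the shift is then about 0.1 to 0.4 SD of change. Over that range, significant improvement under TENS with a non-significant control arm falls from 0.9% to 0.01%. The misleading pattern becomes a significantly worse control arm beside a TENS arm with no significant change. By symmetry with the formula above, with p now the chance of significant worsening:
- d = 0.1: 0.058 × (1 − 0.067) = 0.054
- d = 0.4: 0.341 × (1 − 0.341) = 0.225

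That is about 5% to 22%.

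**The case against.** The strongest reply is that the SAP already plans the right test. Directly after the within-arm tests it specifies the group-by-time ANOVA and says how to read it. A reader might infer that the plan intends to prove TENS by contrasting within-arm p-values. The documents do not support that: nowhere does the SAP say that significance in one arm only shows an effect. This part of the reply stands, and the problem is an unguarded route to a wrong claim in the report. What does not follow is that the route is closed. The rule says when changes differ. It does not say that a non-significant interaction rules out a TENS claim built on the paired tests.

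A second reply is that no favourable shared change is documented. This also stands. The size of any such change is assumed, and at zero the split pattern is no more common than chance. A reader might cite the VAS entry limit as the source of a favourable drift, but it acts in the opposite direction and applies only to VAS.

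A reader might also compound the per-outcome rate over the five listed outcomes to reach a very high chance of at least one false claim. That needs the same favourable change in every outcome, and independent outcomes. The documents support neither; the NDI itself contains a pain-intensity section.

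Finally, one could keep the within-arm tests and only label them descriptive. That would reduce the risk, but a p-value at the common threshold still invites the misreading and adds nothing about TENS.

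**Conclusion.** The point holds as a reporting risk that should be closed. The within-arm tests are planned at the same threshold as the between-arm test and are not subordinated to it, and no rank-based between-arm test of change is named.

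If the split pattern were used to claim a TENS effect, the false-positive rate per outcome would be about 2% to 25%, against 2.5% for an interaction favouring TENS. For VAS the corresponding risk is the worsened-control pattern, at about 5% to 22%. These figures rest on 17 per arm, two-sided 0.05, normal change scores with equal SDs, and an assumed shared change of 0 to 0.7 SD (0.1 to 0.4 SD for VAS). With no shared change there is no excess.

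**What to change.** - Report each arm's mean or median change with its spread, as description only and without p-values.
- State that every conclusion about TENS rests on the between-arm difference in change, from the interaction or a baseline-adjusted ANCOVA, with its 95% CI.
- For non-normal outcomes, compare change scores between arms with a rank-based test, for example Mann-Whitney on change.

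The SAP is in the past tense and already reports a baseline comparison, so the tests appear to have been run. The change therefore applies to the reported analyses and conclusions. It needs no new data and takes nothing from the between-arm comparison. The cost is that significant improvement within an arm can no longer be claimed.

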TENS is the delivery of electrical current through intact skin to stimulate peripheral nerves.²³ TENS delivers electrical currents through the skin with the objective to stimulate peripheral nerves to prevent the transmission of nociceptive information to the brain and by this process achieve pain relief.^{24,25,26,27} One of the most accepted theories for the modulation of pain with the use of TENS is the “gate control theory of pain” by Melzack and Wall published in 1965.^{28,29} which explains pain relief by electrical stimulation.²⁸ The authors proposed that by using electrical currents to stimulate low-threshold A-beta axons, it will reduce pain by preventing the transmission of nociceptive information in the spinal cord and brainstem.²³ This theory also proposed that the substantia gelatinosa (SG) in the dorsal horn of the spine acts as a gate control system before afferents influence T cells.²⁸ T cells then activate the system responsible for response and perception.²⁸ Large-diameter afferent nerve fibers (facilitates SG) and small-diameter afferent nerve fibers (inhibits SG) influence T cells.³⁰ TENS gives the clinician the option to select the depolarization of afferents nerves through the adjustment of parameters of electrical current delivered with electrodes through the skin.³⁰ Depolarizing large-diameter (A-beta) sensory afferent nerves via sensory TENS can help gate or block noxious input.^{30,31,32} TENS has been used for treating subclinical pain based on studies that have found superiority of TENS over placebo for chronic musculoskeletal pain.³³ Most importantly for our study, TENS is a non-prescriptive battery-powered device that uses self-adhering electrodes on the surface of the skin to deliver electrical current. TENS is often self-administered, affordable and safe when compared to medications.²³

Despite electrical stimulation for pain modulation has been used for many years, there is an “efficacy-impasse” for clinical utilization of TENS, despite fifty years of published research.³⁴ There is an urgent need for randomized controlled trials to investigate TENS effectiveness.³⁴ Based on this need the purpose of this study is to investigate the effects of electrotherapy for improving cervical spine proprioception, reduce pain, anxiety, and disability in adults with subclinical neck or upper quadrant pain.

b. Objectives.

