- 1) To measure the immediate and short-term effects of TENS on subclinical neck or upper quadrant pain with the VAS, anxiety with the State-Trait Anxiety Inventory for Adults™, disability with neck disability index (NDI), disability and cervical spine proprioception Noraxon 3D Inertial Motion Capture System in subjects 20-40 years of age.
- 2) To measure pain, anxiety, disability, and cervical spine proprioception in subjects with and without neck or upper quadrant pain.
- 3) To compare compliance of TENS home usage in groups with and without short message system (SMS), text message, reminders.

c. Procedures involved (Research Interventions)

There will be three groups as follows: twenty subjects with no pain in the normal group; forty subjects with chronic subclinical neck or upper quadrant pain will be randomized into two groups: twenty subjects in the control group, and twenty subjects in the intervention group. The intervention group will be further randomized into two groups: ten subjects will receive instructions for home use of TENS with daily SMS text message reminders and ten subjects will receive instructions for home use of TENS without SMS text message reminders. We will aim for an equal distribution of males and females in each group.

First session (Day 1): Before starting the procedures, participants complaining of pain that are greater than 4/10 in the VAS will be excluded from the study as this will be greater of what we consider to be subclinical pain based on literature review and if the pain has been present less than three months. In addition, if participants with pain less than 4/10 pain receiving clinical pain treatment, have taken pain medication

within six hours of first session, have acute pain or contraindications for electrical stimulation would be excluded from the study. Following completion of the signing procedures, all participants will be given brief explanations before administration of the questionnaires.

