9. DATA COLLECTION

The study will be conducted in the Neuroscience Research Laboratory in the SAHP-[name]. Informed consent will be obtained prior to

the beginning of the study by the graduate student investigator and other IRB approved researchers. Participants will be recruited if they are adults (males and females) aged 20-40 years old with no pain for the normal group and with neck or upper quadrant pain no greater than 4/10 in the VAS for longer than three months, not receiving clinical pain treatment, have not taken pain medication within six hours of first session, have acute pain or contraindications for TENS.

Study participants will be assessed on visits one, two and three (visit three will be at the end of the thirty-day period).

During participant's visit one, two and three the following clinical assessments will be provided:

- The VAS for pain, a subjective measure of pain intensity
- The STAI-form Y is a definitive clinical measure of state and trait anxiety in adults.
- The NDI questionnaire that measures neck disability.
- JPE test which will measure cervical spine proprioception through the Noraxon myoMotionTM system instrument.

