13. BENEFIT(S)

We expect that participants will experience improvements in cervical spine range of motion and proprioception, decreased anxiety and neck disability, and all components of improving wholeness and health as participants carry out functional activities. The expected benefits of this study include the improve of quality of life and functional mobility in people with neck chronic pain. In addition, the study may provide evidence of the efficacious use of electrical stimulation as a non-pharmacological option for the management of chronic pain. This study is expected to provide through electrical stimulation an accessible, affordable, self-administered and non-pharmacological option for the management of chronic pain without the need to go to a clinic for the application of electrical stimulation.

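### The SAP tests cervical range of motion on the same footing as the protocol's outcomes, but the protocol never lists it as an outcome or assessment; it should be reported as exploratory

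*SAP*

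**What the plan says.** **SAP.** The single paragraph describes within-group tests of "changes in mean outcome variables (cervical spine AROM, anxiety, neck proprioception, VAS, NDI) over time". AROM comes first in that list and carries no exploratory label. The same paragraph then applies a 2x2 mixed ANOVA (group by time) and, in the intervention group, a three-time-point analysis to the outcome variables in general. Significance is p ≤ 0.05 throughout. The only multiplicity correction is Bonferroni for post hoc comparisons between times. The paragraph also reports a result: "There was a significant difference in mean STAI_T and lateral flexion left between the intervention and control groups at baseline", which led to an ANCOVA.

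**Protocol.** The purpose (section 8a) is to study "the effects of electrotherapy for improving cervical spine proprioception, reduce pain, anxiety, and disability in adults with subclinical neck or upper quadrant pain". Objective 1 (section 8b) names the VAS, the STAI, the NDI and "disability and cervical spine proprioception Noraxon 3D Inertial Motion Capture System". Objective 2 is "To measure pain, anxiety, disability, and cervical spine proprioception in subjects with and without neck or upper quadrant pain". Objective 3 concerns compliance with home TENS. Section 9 introduces its list with "During participant's visit one, two and three the following clinical assessments will be provided" and gives four items: VAS, STAI, NDI and the "JPE test which will measure cervical spine proprioception through the Noraxon myoMotionTM system instrument". The visit-by-visit procedures in section 8c repeat the same four. Neck range of motion appears once, in section 13, where participants are expected to have "improvements in cervical spine range of motion and proprioception".

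**The concern.** An outcome that the analysis plan tests, but that the protocol neither names as an outcome nor describes measuring, cannot be taken as prespecified. Two features of this trial make that matter more than usual. Neither document names a primary outcome, and neither controls error across outcomes. Nothing in the plan therefore stops a significant AROM result from being presented as evidence that TENS works, with the same standing as pain, anxiety, disability or proprioception.

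The SAP's tense adds to the difficulty. It was written after at least the baseline comparison had been run, so it cannot itself serve as evidence that AROM was chosen before data were seen.

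**Working it through.** **1. Outcome lists side by side**

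| Place | Pain | Anxiety | Disability | Proprioception | AROM |
|---|---|---|---|---|---|
| Protocol 8a, purpose | yes | yes | yes | yes | no |
| Protocol 8b, objectives 1 and 2 | yes | yes | yes | yes | no |
| Protocol 8c, procedures | VAS | STAI | NDI | JPE | no |
| Protocol 9, assessments | VAS | STAI | NDI | JPE | no |
| Protocol 13, benefits | no | yes | yes | yes | expected benefit only |
| SAP, outcome variables | VAS | yes | NDI | yes | **yes** |

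The motion-capture system records joint angles, but its only stated use is the JPE test. The protocol gives no AROM procedure, directions or time points. The SAP lists AROM and neck proprioception separately, so AROM is not simply its name for the JPE measure.

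**2. Error across domains**

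The plan gives no error rate across outcomes, so there is no figure of its own to reproduce. The SAP's sample size of 40 does not bear on this point.

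Inputs: alpha 0.05 per test (protocol section 11 and SAP), four protocol domains and five SAP domains. Assumptions: no true effect, and one independent test per domain.

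P(at least one false positive) = 1 − (1 − 0.05)^k

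- k = 4: 1 − 0.95^4 = 1 − 0.8145 = 18.5%
- k = 5: 1 − 0.95^5 = 1 − 0.7738 = 22.6%
- Increase: about 4.1 percentage points

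The outcomes are probably correlated, and the documents give no correlations. A simulation with equal correlation between all outcomes (assumed values) gives:

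| Correlation | 4 domains | 5 domains | Increase (points) |
|---|---|---|---|
| 0.3 | 17.4% | 20.8% | 3.4 |
| 0.7 | 12.9% | 14.8% | 1.9 |

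**3. If AROM is split by direction**

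The number of AROM directions is not stated. For AROM alone, with independent tests:

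- two directions: 1 − 0.95^2 = 9.75%
- six directions: 1 − 0.95^6 = 26.5%, or 24.1% to 16.4% at correlations of 0.3 to 0.7

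These figures show how the risk grows with the number of directions. They do not estimate what was done.

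**The case against.** Four points on the other side have force.

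- **Timing.** A reader might infer that AROM was added once data were available, and that this is outcome-selection bias. The documents do not support that. The past tense dates the SAP's text, not the choice of outcome. Section 13 of the protocol, which is prospective, already expects better range of motion. The SAP compares post with pre, so baseline AROM values exist, and the device that measures joint angles was in use from the first visit. Interest in AROM may well predate the data. This removes the charge of bias but does not supply prespecification: a benefit statement defines no measure, time point or analysis.
- **A changed design.** The SAP describes two groups, 40 participants and a two-week endpoint. The protocol has three groups, 60 participants and visits on Days 8 and 30, and gives no version date. AROM may have come in with a design change, but neither document records one. This is a reason to ask for a dated record, and the fix allows for it.
- **The identity of lateral flexion left.** A reader might take it as an AROM direction, because the SAP labels JPE rotation right as JPE and leaves this variable without that label. That is plausible but not certain. If it is a JPE variable, treating it as AROM would demote a protocol outcome.
- **Size.** A reader might quote 26.5% as the effect of adding AROM. That figure needs six independent directions, a number found in neither document. It also splits AROM while leaving the protocol domains whole, although JPE is reported by direction and the STAI has state and trait scores. The like-for-like change is about 4 points. Most of the error across outcomes is present without AROM, at 18.5% for the four protocol domains.

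**Conclusion.** The discrepancy stands. The SAP tests AROM as an outcome equal to the others, while the protocol never lists it as an outcome or assessment and mentions range of motion only as an expected benefit. Prespecification of AROM cannot be verified from these documents. Outcome selection is therefore a risk they cannot exclude, and nothing in them demonstrates it.

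The effect on error is modest at domain level: from 18.5% to 22.6% under independence with one test per domain, an increase of 1.9 to 3.4 points at assumed correlations of 0.7 to 0.3, and more if AROM is tested in several directions. The larger consequence is interpretive. With no primary outcome, an AROM finding could carry the trial's conclusion although no objective asks about it. The point merits correction but does not undermine the analysis of the four protocol outcomes.

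**What to change.** In the SAP:

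1. Limit efficacy conclusions to the protocol outcomes: VAS, STAI, NDI and JPE.
2. Report AROM in a separate set labelled as not prespecified in the protocol and exploratory, with estimates and confidence intervals. Do not use it to conclude that TENS works. Lift the label only if a dated record from before the data shows that AROM was planned.
3. State whether lateral flexion left is an AROM or a JPE variable. Move its ANCOVA to the exploratory set only if it is AROM.

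Leave section 13 of the protocol unchanged. It is a statement of expected benefit, and it holds the only mention of range of motion in the prospective text.

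The cost is wording in the SAP and the report, with no new data and no loss of information. The downside is that a favourable AROM result can no longer be presented as a main finding. This change does not cure the lack of a primary outcome or of error control across the four remaining domains.
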